#### **Physical activity and Cardiovascular Health**

In T2D, physical activity is an important modifiable risk factor of CVD and increased physical activity has been shown to positively impact cardiovascular health (9). Unfortunately (long-term) compliance to exercise programs in patients with T2D is poor. These programs consist of a combination of aerobic and resistance training for several times a week and most participants quit exercising as soon as the (supervised) exercise intervention ends (10, 11). Most individuals with T2D have led a sedentary lifestyle over decades and they will generally find it difficult swiftly and consistently incorporate participation in exercise programs in their routine. Therefore, for patients with T2D the need to test alternative lifestyle changes that will be actually adopted by these individuals is compelling. From this perspective, it is important to shift our focus from exercise programs to physical activity of daily life or light-intensity physical activity ((LiPA); i.e., standing, walking slowly, household activities or taking a flight of stairs) which may play a crucial role to lower CVD in patients with T2D. Importantly, LiPA has been recognized as also having beneficial effects on cardiovascular health (12) and we have recently shown that high levels of sedentary time are associated with poor health and premature death independent of exercise (13, 14). Furthermore, we have also shown that replacement of sedentary time with LiPA lowers mortality risk (15). Thereby these results point at the importance of LiPA to improve (cardiovascular) health. Finally, LiPA can more easily be incorporated into daily life of sedentary individuals as it is made mainly of activities that are already part of everybody's routine (16-18).

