### **8.1 Primary study parameter(s)**

The effect of the intervention on the primary outcome PWV at month 6 will be analysed using intention-to-treat (ITT) approach according to randomization assignment. The ITT analyses will be used as primary method for our statistical analyses and any outcomes in our reports will be primarily based upon these ITT analyses. In addition, a per protocol analysis will be performed for those who attended the workshops. These analyses will be used to gain some insights into any potential non-response / drop out. These per protocol analyses will not be the primary source for reporting outcomes. General linear models will be used to analyse the effect of the intervention on PWV at month 6. Due to the COVID-19 crisis some month 6 measurement will take place at a later moment, depending on the duration of this delay we will have to adjust for this in our statistical analyses. In addition, repeated measures will be taken into account, baseline, month 3, and month 6 using mixed models in SPSS. The 3-month visits might be missing for some participants due to COVID-19 crisis, we assume that the 6-month measurements for these participants can take place as planned. In these models, subject is entered as a random effect and intervention (categorical variable with 2 levels: 1: intervention; 2: control group) as a fixed effect. The baseline value of PWV and sex will be used as covariates in analyses.

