### **8.2 Secondary study parameter(s)**

Sedentary time, as measured by the activPAL will be analysed as total sedentary minutes on an average day as well as the percentage of sedentary during wake time. Similarly, time standing and stepping, also derived from the activPAL data will be analysed. All metabolic health parameters and microcirculation measurements will also be analysed as continuous

variables. Quality of life and mental functioning are also analysed as continuous variables. Finally, measures of body composition measures are also all continuous outcomes variables

Similar to the primary outcome analyses, general linear mixed models will be used to analyse the change in the secondary outcome measures from baseline to month 6. Using mixed models, the repeated measures will be taken into account similar to the analyses with the primary outcome.

All analyses, for the both primary and secondary outcomes will also be conducted for the follow-up (month 12 data) to examine the long-term effect of the intervention, taking into account all repeated measures (baseline, month 3, month 6) in a mixed model.

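### The mixed model has no visit or intervention-by-visit term, so its intervention coefficient averages over visits and is not the month-6 or month-12 effect

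*Protocol*

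**What the plan says.** Section 8.1 of the protocol first names a general linear model for PWV at month 6. It then adds a second model: "repeated measures will be taken into account, baseline, month 3, and month 6 using mixed models in SPSS". The terms of that model are listed: "subject is entered as a random effect and intervention (categorical variable with 2 levels: 1: intervention; 2: control group) as a fixed effect". The covariates follow: "The baseline value of PWV and sex will be used as covariates in analyses".

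Section 8.2 extends the mixed model in two directions.

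- **Secondary outcomes:** "general linear mixed models will be used to analyse the change in the secondary outcome measures from baseline to month 6", and "the repeated measures will be taken into account similar to the analyses with the primary outcome". No other method is named for these outcomes.
- **Month 12, all outcomes:** the analyses "will also be conducted for the follow-up (month 12 data) to examine the long-term effect of the intervention". The method given there is again a mixed model, and the visits it lists are baseline and months 3 and 6.

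Neither a visit term nor an intervention-by-visit term appears anywhere in section 8. Baseline is listed both as one of the repeated measures and as a covariate.

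**The concern.** A model with one intervention coefficient and no interaction with visit assumes the same arm difference in every response row and estimates their average. The protocol asks for something else: the effect at month 6 and, separately, whether anything remains at month 12.

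The two questions are harmed differently. For the secondary outcomes, the coefficient can misstate the month-6 effect, usually towards zero. For month 12, differences seen during the intervention are pooled into a result labelled long-term, so a significant finding can arise when nothing is left at month 12.

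An effect that changes over time is realistic here. In section 5.1 phone support tapers over the first three months and then stops, and the last six months are unsupervised. The introduction says of exercise programmes that "most participants quit exercising as soon as the (supervised) exercise intervention ends".

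**Working it through.** **Inputs**

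- From section 4.4: a 10% difference in PWV, alpha 0.05 (two-sided by the printed formula), power 80%, 73 per group, 80 enrolled per group, about 10% drop-out. This leaves 80 × 0.9 = 72 per arm.
- Not in the protocol, so assumed: the coefficient of variation (CV), the correlation between visits (0.7, range 0.5 to 0.8, compound symmetry) and the time course of the effect.
- CV back-solved from the stated sample size, with 2.802 as the sum of the two normal quantiles: sqrt(73 × 0.10² / (2 × 2.802²)) = 0.216. The 73 cannot be reproduced independently, because no mean or SD is given. The averaging argument does not depend on it.

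**What the coefficient estimates**

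With complete, balanced visits and only subject-level terms, the random-intercept estimate equals a regression on each subject's mean over the response rows. Write d3, d6 and d12 for the true arm differences at months 3, 6 and 12. The expected difference at baseline is 0.

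- Month-6 model, baseline as covariate only: (d3 + d6)/2
- Month-6 model, baseline as a response row: (0 + d3 + d6)/3
- Month-12 model, baseline as covariate only: (d3 + d6 + d12)/3
- Month-12 model, baseline as a response row: (0 + d3 + d6 + d12)/4

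The month-12 formulas take month 12 as a response row alongside the visits listed in section 8.2.

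**Month 6, true effect 10%**

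| Pattern | Baseline covariate only | Baseline a response row |
|---|---|---|
| Full effect already at month 3 | (10+10)/2 = 10% | 20/3 = 6.7% |
| Linear build (5% at month 3) | (5+10)/2 = 7.5% | 15/3 = 5.0% |
| Effect only at month 6 | (0+10)/2 = 5.0% | 10/3 = 3.3% |

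Simulation at correlation 0.7 (3,000 runs per case) gave 10.0, 7.5 and 5.0 with baseline as covariate only, and 6.7, 5.0 and 3.4 with baseline as both covariate and response row. There is no dilution if d3 = d6 (covariate only) or d3 = 2 × d6 (response row). Beyond those points the effect is inflated.

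**Month 12, true month-12 effect zero**

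With baseline as covariate and three post-baseline visits at correlation r, the residual variance of the subject mean is CV² × [(1 + 2r)/3 − r²]. At r = 0.7 the bracket is 0.80 − 0.49 = 0.31, so SE = 21.6 × sqrt(0.31 × 2/72) = 2.00 percentage points.

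- 10% at months 3 and 6 (an illustrative extreme): estimate 20/3 = 6.7%, z = 3.33, rejection Φ(3.33 − 1.96) = 91%.
- 5% at months 3 and 6: estimate 10/3 = 3.3%, z = 1.66, rejection Φ(1.66 − 1.96) = 38%.
- 5% at month 6 reached linearly: estimate 7.5/3 = 2.5%, rejection 24%.

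At r = 0.5 the SE is 2.32 and at r = 0.8 it is 1.71. Over that range the three rejection rates run 82–97%, 30–49% and 19–31%. Simulation (5,000 runs at r = 0.7) gave 91.2% and 38.5% for the first two.

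If baseline is both a covariate and a response row, the coefficient and its SE both shrink by k/(k+1), with k post-baseline visits. The estimates become 5.0% and 2.5%, but the test is unchanged. If baseline is a response row and not a covariate, the variance factor is (1 + 3r)/4. The rates then fall to 35% and 12% at r = 0.7 (33–42% and 12–14% over the range).

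**No effect at any visit**

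Simulated rejection was 4.2% to 5.4% under all readings of baseline, so type I error under the global null is near nominal.

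**The case against.** The protocol does not say that its list of terms is complete. Visit terms are often left to an analysis plan, and section 8.2 speaks of change from baseline to month 6, which hints that some time term was intended. It is also arguable that the month-12 sentence, which covers all analyses, repeats the general linear model for PWV at month 12. The 10% effect and the CV are PWV planning values, not values for the secondary outcomes. The introduction's remark on quitting concerns supervised exercise, which the protocol contrasts with light activity that it expects to last.

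Some of this stands. The numbers illustrate a mechanism and do not forecast any particular outcome, and the 91% needs a strong, sustained effect that then vanishes completely. Waning is plausible, not established.

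The rest does not remove the point. The protocol goes well beyond naming a mixed model: it gives the visits, the random effect, the fixed effect with its coding, and the covariates. Anyone following that text obtains an averaged coefficient. That the stated target needs a time term shows the mismatch and does not cure it. The month-12 sentence ends by specifying a mixed model, and a general linear model reading would in any case rescue only PWV. A statistician who silently adds visit terms departs from the written plan and still has no named contrast to report.

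**Conclusion.** The concern holds. As written, the mixed model estimates a visit-averaged arm difference, not the month-6 change set as the target for the secondary outcomes or the long-term effect at month 12. That conclusion follows from the listed terms and needs no assumption about variance or correlation.

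Its size does depend on assumptions. For effects that appear between month 3 and month 6, the coefficient is 50% to 100% of the month-6 effect with baseline as covariate only, and 33% to 67% with baseline as a response row. For month 12 with no remaining effect, false long-term findings range from about 12% to 97% of trials across the scenarios examined. They are about 38% for a sustained 5% on-intervention effect at correlation 0.7 with baseline as covariate. These rates assume 72 per arm, CV 21.6%, complete data and compound symmetry.

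The general linear model for PWV at month 6 is not affected. The problem lies in what the secondary and follow-up analyses estimate, and it should be fixed before analysis.

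**What to change.** Amend sections 8.1 and 8.2 as follows.

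1. Give baseline one role: either a covariate with only post-baseline visits as response rows, or a response row with the arm means constrained equal at baseline. Do not use both.
2. Add visit as a categorical fixed effect, and the intervention-by-visit interaction.
3. Name the arm contrast at month 6 as the month-6 result and, separately, the arm contrast at month 12 as the long-term result. Include month 12 explicitly among the visits of the follow-up model.

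The covariance structure and any baseline-by-visit term can be left to the statistician. The cost is two or three sentences. The model runs in SPSS MIXED and needs no new data.

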### **8.2 Secondary study parameter(s)**

Sedentary time, as measured by the activPAL will be analysed as total sedentary minutes on an average day as well as the percentage of sedentary during wake time. Similarly, time standing and stepping, also derived from the activPAL data will be analysed. All metabolic health parameters and microcirculation measurements will also be analysed as continuous

variables. Quality of life and mental functioning are also analysed as continuous variables. Finally, measures of body composition measures are also all continuous outcomes variables

Similar to the primary outcome analyses, general linear mixed models will be used to analyse the change in the secondary outcome measures from baseline to month 6. Using mixed models, the repeated measures will be taken into account similar to the analyses with the primary outcome.

All analyses, for the both primary and secondary outcomes will also be conducted for the follow-up (month 12 data) to examine the long-term effect of the intervention, taking into account all repeated measures (baseline, month 3, month 6) in a mixed model.

## **9. ETHICAL CONSIDERATIONS**

### **9.1 Regulation statement**

LiPAT will be conducted according to the principles of the Declaration of Helsinki (version 2013 ([www.wma.net](http://www.wma.net))) and in accordance with the Medical Research Involving Human Subjects Act (WMO); [www.wetten.overheid.nl/BWBR0009408/2015-12-17](http://www.wetten.overheid.nl/BWBR0009408/2015-12-17))).

### **9.2 Recruitment and consent**

The initial information about LiPAT will be passed on to the potential participant via advertisements (see attachment) and a general invitational letter (see appendix) distributed freely via the outpatient-clinic (information display) and the GP's waiting room (information display). There is no active role for the potential participants own consultant or GP in LiPAT recruitment and they will not receive any recruitment fees. If any potential participant then contacts us, either by telephone or email, the initial LiPAT telephone interview will be held to determine preliminary eligibility. Each potential participant will be informed about the consequences of participating in the study for his or her personal life.

From then onwards the participant will follow the logistics as described in section 3.2. Briefly, after the telephone interview the potential participant will be send an envelope containing the invitation letter (see appendix) including the informed consent form and an appointment will be made for the baseline visit. We aim for a time window between the telephone interview and the baseline visit of minimally 1 week which will give the participant the opportunity to think over his/her participation and if necessary discuss any topics with family, friends, general practitioner of the independent doctor attached to this trial (please see appendix). The baseline namely consists of two parts. Part A is strictly part of the inclusion procedure. During this part a standard physical examination will take place and an ultrasound scan will be performed to screen for large atherosclerotic plaques of the carotid arteries (see below). The participant will be informed that the outcome of this first part of the visit may still to exclusion. If then the participants is indeed eligible part B will take place in which the investigational baseline measurements are performed. After the above procedure randomization will take place. From then on participants will run through the protocol either being part of the intervention or control group. The informed consent procedure and physical examination of the base line visit will be performed by both the principal investigator (PhD-student who holds and MD – [name])

### 9.3 Benefits and risks assessment, group relatedness

LiPAT will not recruit minors and(or) incapacitated adults. The age range of the study population will be 40 to 70 years.

#### *Health check-up*

To a certain extent, LiPAT will offer its participants an extra outpatient clinic check-up at 4 moments in time. LiPAT has decided that results of these standard tests should be communicated with the participant, as they may lead to any adjustments in their care (e.g., any weight loss might result in adjustment of an insulin regimen). Communicated to the participant will therefore be: glucose, HbA1c, lipid profile, urine (albuminuria), next to standard findings from the physical examination (e.g., weight). The above tests would also be part of standard or routine care procedure for those with diabetes at e.g., their general practitioner.

#### *Risks of specific measurements*

For LiPAT only non-invasive low risk study procedures will be performed. The investigational research team hold the opinion that the current protocol subscribes to the above and considers the risk for any adverse events due to the different study procedures low. Nevertheless it cannot wholly be excluded, that behavioural changes with regard to any changes in movement patterns may lead to unforeseen adverse events. LiPAT considers the risks in light of the recruited study population nevertheless acceptable.

#### *Time and inconvenience*

A possible burden for the participant is that LiPAT (and especially the intervention arm) may be intrusive, as the Fitbit inspire allows for continuous feedback (also by giving timed reminders). It will be possible however to turn such reminders off and from month 4 to 6 feedback is entirely voluntarily and digital.

### 9.4 Compensation for injury

The sponsor/investigator has a liability insurance which is in accordance with article 7 of the WMO. The sponsor (also) has an insurance which is in accordance with the legal requirements in the Netherlands (Article 7 WMO). This insurance provides cover for damage to research subjects through injury or death caused by the study. The insurance applies to the damage that becomes apparent during the study or within 4 years after the end of the study.

### **9.5 Incentives (if applicable)**

Each participant will receive a sum of € 80 compensation for their invested time and travel expenses. If travel expenses for a participant exceed the amount of 80EUR, this will be reimbursed . If a participant drops out before completion of all four study visits he will be reimbursed € 10 per visit fulfilled.

## **10. ADMINISTRATIVE ASPECTS, MONITORING AND PUBLICATION**

### **10.1 Handling and storage of data and documents**

Study data will be entered in Castor (<https://www.castoredc.com/>) a save cloud based electronic data capture platform that is supported by MEMIC. At the end of the study data can be exported for analyses. The central database consists of two separate components: Section 1 contains personal information on the participants entered in Idot and is physically separate from the research results. This section records and stores a participant's ID and personal information, such as name, address and contact information. This section is also responsible for monitoring consent forms. The file does not contain research information and capable of meeting the logistical requirements.

Section 2 contains the research results (Castor) with the corresponding participant-specific ID code and is only accessible to the investigational team. This file contains all registered research results such as questionnaire data, physical examination information and imaging research. It also records which researcher conducted the measurements and whether any adjustments were made. The key to the ID code will be under the charge of the principal investigators of LiPAT. Data will be stored in this fashion for 15 years after the end of the study. We state explicitly that the following parties will have access to the data next to all primary investigators of LiPAT themselves, governmental parties from the ministry of Health (e.g., Inspectie voor de Gezondheidszorg (or others if obliged to do so by law)), trial monitors (e.g, CTCM) and METC-members.

With regard to the remainders of the blood samples after determination of the primary laboratory variables, these will be stored, under their ID-code, in a MUMC+ owned biobank for a period of 15 years after the end of the study.

We state explicitly that the following parties will have access to the biodata next to all primary investigators of LiPAT themselves, governmental parties from the ministry of Health (e.g., Inspectie voor de Gezondheidszorg (or others if obliged to do so by law)), trial monitors (e.g, CTCM) and METC-members.

In order to be able to determine any potential (future) (bio-)markers that might be associated with any changes in physical activity. If any such question would arise additional approval will be sought from the METC/MUMC+. Participants have to specifically approve the uptake of their samples in this biobank. The participants will however not be asked extra permission for any future analyses upon this material.

Data may also be shared with industrial partners. Participants of LiPAT will have to specifically approve their permission to do so via the informed consent form. Criteria for such a partnership include that the data are used for scientific research, which may include

development or validation of algorithms (e.g., to further develop any sedentary behaviour identification algorithms). An agreement with business partners will be made about sharing of data in which at least the rights of the donor are warranted. Data that are shared, if any, will always be coded, according to the above, in order to protect the privacy of participants. No personal details of any of the participants will be handed over to any industrial partner.

### **10.2 Monitoring and Quality Assurance**

Monitoring will take place by CTCM.

### **10.3 Amendments**

Amendments are changes made to the research after a favourable opinion by the accredited METC has been given. All amendments will be notified to the METC that gave a favourable opinion.

All substantial amendments will be notified to the METC and to the competent authority.

Non-substantial amendments will not be notified to the accredited METC and the competent authority, but will be recorded and filed by the sponsor.

### **10.4 Annual progress report**

The sponsor/investigator will submit a summary of the progress of the trial to the accredited METC once a year. Information will be provided on the date of inclusion of the first subject, numbers of subjects included and numbers of subjects that have completed the trial, serious adverse events/ serious adverse reactions, other problems, and amendments.

### **10.5 Temporary halt and (prematurely) end of study report**

The investigator/sponsor will notify the accredited METC of the end of the study within a period of 8 weeks. The end of the study is defined as the last patient's last visit.

The sponsor will notify the METC immediately of a temporary halt of the study, including the reason of such an action.

In case the study is ended prematurely, the sponsor will notify the accredited METC within 15 days, including the reasons for the premature termination.

Within one year after the end of the study, the investigator/sponsor will submit a final study report with the results of the study, including any publications/abstracts of the study, to the accredited METC.

